### 10.3.3 Research Design

Participants (aged 50 – 65; either sex, all ethnicities) will be recruited from local hospitals and clinics by various means, including physician referral or by response to flyer advertisements (see section 10.3.5). Potential participants will be screened over the phone regarding their possible inclusion in the study (see inclusion/exclusion criteria below). Among other things, participants will be asked if they have received a medical diagnosis of idiopathic PD from a neurologist, and if they have been medically cleared to participate in exercise by a physician.

On day one, participants will come to the Exercise Science laboratory at Idaho State University in Meridian. The PI will obtain informed consent and will complete patient screening according to our IRB approved research plan. Participants will be verbally asked for demographic information including name, contact information, ethnicity, age, gender, weight, height, and number of falls experienced over the past 3 months. Subjects will also take the Montreal Cognitive Assessment, which is a brief screening tool that provides a quantitative assessment of cognitive impairment. The Hoehn & Yahr scale will be used to identify Parkinson's disease stage. Participants meeting the inclusion criteria will be enrolled in the study and will undergo the baseline outcome assessments, which are described in the Section 10.3.4 below.

The intervention will take place at the Caldwell YMCA and consist of 12 weeks of exercise, guided by four certified personal trainers at the YMCA who are trained to work with individuals with neurologic conditions such as PD. All trainers have been trained to safely and effectively perform the balance activities that will be employed throughout the program. The head trainer has received a specialty certification in the boxing training program utilized in this study. A version of the proposed exercise program has been validated in a group of persons with PD previously. Our incorporation of balance training activities into the program introduces a novel and essential ingredient for fall reduction to the program.

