#### 10.3.4 Outcome Measures

Outcome assessments will take place at baseline (i.e., approximately 1 week before the beginning of the training program (T0)), at 6 weeks (T6), and 1 week after the completion of the 12 week training program (T12), as well as 3 months after the training program. All of the outcome assessments up to T12 will be performed by the PI at the Exercise Science Lab while the participants are on their standard course of medication. Motor dysfunction will be assessed at baseline using the motor section of the Unified Parkinson's Disease Rating Scale (UPDRS). The functional balance outcomes include: the mini BEST test (results of which will be shared with trainers at the YMCA for group assignment), the Activities-Specific Balance Confidence (ABC) scale, the Berg Balance Scale (BBS), the Timed Up and Go (TUG), and the Functional Reach Test (FRT). The kinematic outcomes from the hips, knees, and ankles of both limbs will be gathered using the VSTBalance during a straight line gait assessment at a self-selected pace. The infrared camera will identify the length of each lower-extremity segment (femur, tibia, foot) to derive the precise angular displacement (range of motion) occurring at the hip, knee, and ankle joints of each limb.

For Aim #1 we will be assessing the relationship between modifiable factors and outcomes on mobility assessments. We will compare individual characteristics as follows to identify if they are related to the balance outcomes in our model: gait characteristics (stride length, step length etc), motor dysfunction on UPDRS, lower-extremity joint kinematic range of motion, and balance domain dysfunction at baseline. For Aim #2 we will be asking individuals at baseline to self-report the number of falls they have had during the previous 3 months. We will send a prepaid postcard in the mail 3 months after the completion of the training intervention, asking participants to report the number of falls they have experienced since the training ended.

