#### 10.3.6 Sample size and Statistical analysis

Aim# 1 is the primary aim and based on our preliminary data with alpha=.05, a sample size of 20 will give 84% power to detect a relationship with an effect size of  $r=.60$ . The prevalence of PD in industrialized countries is estimated to be about 0.3%. Using this estimation, we anticipate there to be approximately 2,129 persons in the Boise area with PD. Based on these factors we anticipate fully meeting our recruitment needs.

For Aim #1, the goal is to explore the relationship between modifiable factors and outcomes. Initially because of the exploratory nature of these explorations, change scores for the outcome measures will be

constructed. Bi-variate correlations, parametric and non-parametric as appropriate, will be used to assess the strength of the relationship between individual outcome change scores and the modifiable factors. These results may be confounded by the progression of the disease, especially at the later measurement. Change in disease state will be introduced as a possible influence in partial correlations between modifiable factors and outcomes. Effect sizes will be calculate using Cohen's  $d$ .

For Aim #2 the interest is in the reduction of falls among this patient population. Initially to examine the changes in the number of falls a non-parametric McNemar test of change will be used. To examine other factors outside of the intervention that could influence the outcome will follow-up the analyses with McNemar test stratified by possible confounders (i.e. progression of the disease, continuation of the exercise regimen).

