### 10.3.7 Expected Outcomes

At the completion of this investigation we expect to find that improvements in functional mobility following community-based exercise will be driven by stage of motor dysfunction, peak lower-extremity joint angular displacement, and balance domain dysfunction at baseline (**Aim #1**) (Table 2). These findings will enable a revolutionary approach to rehabilitation for persons with PD, by targeting rehabilitation techniques focused on each individual's modifiable risk factor(s). Finally, we expect to find that by focusing our intervention on the domain of balance dysfunction that is most impaired in individual participants, we will reduce fall incidence (**Aim #2**). This will be a hallmark finding for the treatment of PD, as therapies thus far have been refractory to fall reduction.

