## 10.4 Potential Problems & Alternative Approaches

One potential problem with this clinical trial is that dropouts may occur. Our prior experience with longitudinal exercise studies suggests that we can expect a dropout rate between 5-20%. We have anticipated a very conservative 20% rate, and will recruit 4 additional participants over our sample size of 20. This will ensure an appropriate number of subjects completing the study to maintain the desired statistical power.

While we are attempting to limit the variability in participant outcomes by constraining inclusion criteria to persons with mild to moderate PD, this also poses a challenge in that many participants who volunteer for exercise studies are likely to be physically active individuals, which has the potential to dilute our treatment effect. This recruitment bias may also mean that few of these individuals will have experienced falls at baseline. In the event that non-statistically significant results appear, we have planned our analysis such that we can utilize clinically significant outcomes (eg., effect sizes) to overcome any potential recruitment bias and demonstrate the clinical impact of the intervention.

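### Aim #2 tests a change in the number of falls with McNemar's test, which takes only paired yes/no data, and no faller cut-off is defined

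*Protocol*

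**What the plan says.** Falls are recorded as a number at both time points. Protocol section 10.3.3 asks at the first visit for the "number of falls experienced over the past 3 months". Section 10.3.4 has participants "self-report the number of falls they have had during the previous 3 months" at baseline, then sends a postcard three months after training "asking participants to report the number of falls they have experienced since the training ended".

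The aim is also about quantity. Section 10.3.6 states: "For Aim #2 the interest is in the reduction of falls among this patient population". Section 10.3.7 expects that "we will reduce fall incidence".

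The analysis in section 10.3.6, repeated word for word in the SAP, is: "Initially to examine the changes in the number of falls a non-parametric McNemar test of change will be used". The follow-up analysis is a "McNemar test stratified by possible confounders (i.e. progression of the disease, continuation of the exercise regimen"). Neither document says which version of the test is meant or whether it is one- or two-sided. Section 10.4 warns that recruitment bias may mean that "few of these individuals will have experienced falls at baseline".

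**The concern.** McNemar's test compares the two kinds of discordant pair in a paired binary table: people who change from yes to no, and people who change from no to yes. It cannot take a count. Someone must first choose a threshold, and in the text available nobody has. The choice could therefore be made after the data are seen.

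Once a threshold is chosen, the question changes. With any fall as the threshold, a participant who goes from eight falls to four counts as unchanged. A real reduction among people who continue to fall is invisible to the test, although that reduction is what the aim describes.

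**Working it through.** **Stated figures.** The plan gives no power for Aim #2. Its only power figure is 84% for the Aim #1 correlation (n=20, r=.60, alpha .05). This reproduces at 83.5% two-sided by bivariate-normal simulation and is not affected by this point.

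**1. What the undefined cut-off does.** A constructed example: 20 people, of whom 8 fall, with counts 6, 4, 8, 2, 4, 6, 2, 10. Every count halves, so the total goes from 42 to 21.
- McNemar, cut-off 1 or more falls: 0 discordant pairs, p = 1.0.
- McNemar, cut-off 2 or more falls: the two people going from 2 to 1 are discordant, 2/0, p = 2 × 0.5² = 0.50.
- Exact Wilcoxon signed-rank on the counts: all 8 differences in one direction, p = 2 × 0.5⁸ = 0.0078.

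**2. Smallest reachable p-value.** With k discordant pairs all one way:
- Exact two-sided: p = 2 × 0.5^k. k=5 gives .0625 and k=6 gives .031, so at least 6 are needed.
- Uncorrected asymptotic: chi-square = (k−0)²/k = k on 1 df. k=3 gives .083 and k=4 gives .046, so at least 4 are needed.

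**3. Power under assumed fall rates.** The documents give none. Assumptions: n=20; gamma-Poisson counts with a frailty shared by both windows (shape 0.5 to 1); every rate halved; two-sided .05; McNemar on any fall; zero differences dropped in the Wilcoxon test; 6,000 simulated trials per scenario. Ranges run over the shape parameter.

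| Mean falls per 3 months before training | Exact McNemar | Exact Wilcoxon | Uncorrected asymptotic McNemar | Asymptotic Wilcoxon, tie-corrected | Trials with fewer than 6 discordant pairs | Of those whose falls decrease, share who still fall |
|---|---|---|---|---|---|---|
| 0.25 | 2-3% | 3-4% | 10-12% | 8-10% | 68-80% | 5-9% |
| 0.5 | 4-8% | 10-12% | 14-17% | 18-19% | 34-59% | 14-20% |
| 1 | 7-11% | 26-31% | 17-21% | 33-37% | 20-48% | 30-36% |
| 2 | 8-12% | 52-60% | 19-24% | 56-62% | 29-54% | 49-53% |

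The last column gives the mechanism: these people improve but count as no change. With no true change, exact Wilcoxon rejects in 1-5% of trials and exact McNemar in 1-2%, so the gain is not bought with false positives.

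**4. A model less favourable to the count test.** Some fallers stop altogether and 5% of non-fallers start. With one fall per faller, the two exact tests have identical power. With repeat fallers (1 + Poisson(1.5) falls, redrawn if they continue):

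| Fallers at baseline | Share who stop | Exact McNemar | Exact Wilcoxon |
|---|---|---|---|
| 20% | half | 0.6% | 2.6% |
| 40% | half | 13% | 22% |
| 60% | half | 46% | 44% |
| 60% | three quarters | 84% | 82% |

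**5. The stratified follow-up.** It can be read in more than one way.
- *Separate tests per stratum.* By step 2, a stratum of fewer than 6 people (exact) or fewer than 4 (uncorrected asymptotic) cannot reach p<.05. In a stratum of 10 where half of the fallers stop, exact power is 0.01%, 0.6% and 4.3% with 20%, 40% and 60% fallers. The uncorrected asymptotic test gives 1.0%, 9.8% and 30%.
- *One pooled test (Mantel-Haenszel form).* It sums the same discordant pairs. Strata 4/1 and 3/2 give (3+1)²/(5+5) = 1.6. Unstratified, 7/3 gives (7−3)²/10 = 1.6. It adjusts for nothing.
- *A comparison of change between strata.* The wording allows this too, but McNemar's test is not a test of that difference.

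**The case against.** The strongest reply is that the large gains need fall rates that the plan gives little reason to expect. Section 10.3.5 restricts entry to ages 50-65 and Hoehn & Yahr stages 1.0-3.0, and section 10.4 expects active volunteers with few falls. At a mean of 0.25 falls the choice of test makes almost no difference, and in two of the four repeat-faller scenarios in step 4 exact McNemar is slightly ahead. This stands: the size of the loss is conditional.

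Aim #2 is also not the primary aim. Sample size and power rest on Aim #1, and section 10.4 plans to rely on effect sizes if results are not significant. This limits the weight of the point but does not make the named test fit the data.

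McNemar's test is valid for a change in the proportion of fallers, so defining a faller and restating the Aim #2 endpoint would also remove the contradiction. That is true and is the smaller edit. It would, however, give up the counts already being collected and narrow an aim that sections 10.3.6 and 10.3.7 state as fewer falls.

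Finally, parts of both documents are not available, and a faller definition could sit there. The statement about the cut-off is limited to the text that can be read. A definition elsewhere would settle the threshold but would not make McNemar a test of the number of falls.

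**Conclusion.** The concern holds. The mismatch between a count endpoint and a paired binary test follows from the text alone and needs no assumption. As written, the Aim #2 analysis either cannot be run or answers a different question.

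The consequence depends on assumed fall rates. If participants average 1 to 2 falls per 3 months and a halving leaves many still falling, a paired count test has roughly two to seven times the power of exact McNemar (26/11 ≈ 2.4 at the least, 60/8 = 7.5 at the most). Uncorrected asymptotic McNemar still reaches only 17-24%. If few people fall, both tests have little power and the gain is negligible. The plan should be corrected before analysis, with the weight due to a non-primary aim.

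**What to change.** Replace the Aim #2 paragraph in both documents with text such as:

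> The paired change in number of falls (3 months before baseline versus since training ended) will be tested with a two-sided exact Wilcoxon signed-rank test that handles ties, with zero differences dropped. This p-value governs the conclusion. The post/pre fall rate ratio with 95% CI will be estimated with a Poisson GEE clustered on participant (small-sample-corrected robust SE, t reference with n−1 df). If the two recall windows differ in length, the test will use falls per week of recall and the model will use log window length as an offset. If one window has no falls, totals will be reported without a ratio. Faller status (0 versus 1 or more falls) is secondary, tested with two-sided exact McNemar. Results will be shown descriptively by disease progression and by exercise continuation, without separate tests within strata.

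The p-value rule is needed because the Wilcoxon test and the GEE interval disagree at .05 in about 10-18% of simulated trials at means 0.5 to 2. The window clause is needed because the postcard period stays open until the participant answers. If replies come 0-4 weeks after a 13-week window (an assumed delay), an uncorrected ratio reads 0.57 for a true 0.50; with the offset it reads 0.49-0.51.

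The cost is wording and a minor extra analysis of data already collected. No patients, visits or assessments are added, but the date of each returned postcard must be kept. There are three downsides:
- Power stays low if falls are rare: 3-4% at a mean of 0.25, below the 10-12% of an uncorrected asymptotic McNemar.
- About 2 points are lost against exact McNemar if 60% fall repeatedly and many stop.
- The ratio could not be computed in 10-12% of simulated trials at a mean of 0.25.

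If the sponsor prefers to keep McNemar as the main test, the minimum is to fix the cut-off, test version and sidedness in advance, and to restate Aim #2 as a change in the proportion of fallers.

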10.3 Approach

10.3.6 Sample size and Statistical analysis

Aim# 1 is the primary aim and based on our preliminary data with alpha=.05, a sample size of 20 will give 84% power to detect a relationship with an effect size of $r=.60$. The prevalence of PD in industrialized countries is estimated to be about 0.3%.¹ Using this estimation, we anticipate there to be approximately 2,129 persons in the Boise area with PD. Based on these factors we anticipate fully meeting our recruitment needs.

For Aim #1, the goal is to explore the relationship between modifiable factors and outcomes. Initially because of the exploratory nature of these explorations, change scores for the outcome measures will be constructed. Bi-variate correlations, parametric and non-parametric as appropriate, will be used to assess the strength of the relationship between individual outcome change scores and the modifiable factors. These results may be confounded by the progression of the disease, especially at the later measurement. Change in disease state will be introduced as a possible influence in partial correlations between modifiable factors and outcomes. Effect sizes will be calculate using Cohen's d .

For Aim #2 the interest is in the reduction of falls among this patient population. Initially to examine the changes in the number of falls a non-parametric McNemar test of change will be used. To examine other factors outside of the intervention that could influence the outcome will follow-up the analyses with McNemar test stratified by possible confounders (i.e. progression of the disease, continuation of the exercise regimen).

Reference

1. de Lau LM, Breteler MM. Epidemiology of Parkinson's disease. *The Lancet Neurology*. Jun 2006;5(6):525-35. doi:10.1016/s1474-4422(06)70471-9

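### The Aim #2 follow-up looks for outside influences on falls with stratified McNemar tests, which do not compare the strata and give no adjusted result

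*Protocol*

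**What the plan says.** Section 10.3.6 of the protocol gives the main Aim #2 analysis: "Initially to examine the changes in the number of falls a non-parametric McNemar test of change will be used". The follow-up has a stated purpose and a stated method. The SAP, section 10.3.6, repeats it in the same words: "To examine other factors outside of the intervention that could influence the outcome will follow-up the analyses with McNemar test stratified". The factors are named in the phrase "McNemar test stratified by possible confounders (i.e. progression of the disease, continuation of the exercise regimen").

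Falls are self-reported at baseline for the preceding 3 months. They are reported again on a postcard sent 3 months after training, "asking participants to report the number of falls they have experienced since the training ended" (protocol 10.3.4). Section 10.4 warns: "This recruitment bias may also mean that few of these individuals will have experienced falls at baseline".

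Neither document gives a between-stratum comparison, an adjusted model for falls, a definition of the strata, or a rule for reading the stratum results.

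**The concern.** Whether progression or continued exercise influences the fall change is a question about a difference: did falls change more in one group than in the other? The planned test answers another question, whether there was any change within a group. Two strata can give p-values on opposite sides of .05 while their changes are almost the same. Both can also lose significance merely because each holds half the participants.

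The word confounder does not fit well either. Each participant is his or her own control, so sorting participants into groups does not adjust the before-after comparison. Both factors also arise after baseline.

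At stake is how the fall result is interpreted. Protocol 10.3.7 expects fall reduction to be a major finding, and 10.5 says the aims lay the foundation for a randomised trial.

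**Working it through.** **Inputs from the documents.** About 20 completers: "We have anticipated a very conservative 20% rate, and will recruit 4 additional participants over our sample size of 20" (protocol 10.4). Alpha .05 is stated for Aim #1 ("based on our preliminary data with alpha=.05") and is assumed here, two-sided, for Aim #2. The only power figure is 84% for r = .60 with n = 20. It roughly reproduces (83.1% from a bias-corrected Fisher z with the t critical value, 83.5% by simulation), but it concerns Aim #1. Aim #2 has no power statement.

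**Assumptions, not in the documents.** McNemar is applied to faller versus non-faller status. There are two strata of 10. In both, the same proportion stop falling (20% to 50%) and 5% start. The strata therefore do not differ in truth.

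**Step 1: can a stratum reach significance?** If b participants stop and c start, the exact test refers min(b, c) to a binomial with b + c trials and probability 1/2. With 5 stopping and 0 starting, p = 2 × 0.5^5 = .0625. With 6 and 0, p = 2 × 0.5^6 = .031. So at least 6 of 10 must change, and if exactly 6 change, all must go the same way. A stratum with five or fewer baseline fallers cannot show a significant reduction.

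**Step 2: how often do identical strata appear to differ?** If p is the chance that one stratum of 10 is significant, exactly one of two is significant with probability 2p(1 − p). At 40% stopping, p = .124 and 2 × .124 × .876 = .217. The last column is from full enumeration.

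| Stop falling | Overall test significant (n = 20) | One stratum significant (n = 10) | Exactly one stratum significant | Neither significant, given overall significant |
|---|---|---|---|---|
| 20% | 9.5% | 0.5% | 1.0% | 92% |
| 30% | 32.1% | 3.6% | 7.0% | 80% |
| 40% | 58.2% | 12.4% | 21.7% | 62% |
| 50% | 78.5% | 27.4% | 39.8% | 42% |

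At 10% stopping, exactly one stratum is significant in 0.02% of trials.

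**Step 3: sensitivity.** For 20%, 30%, 40% and 50% stopping, a 14/6 split gives exactly one significant stratum in 2.7%, 13.7%, 33.0% and 54.2% of trials. Uncorrected chi-square McNemar with a 10/10 split gives 15.4%, 36.2%, 48.4% and 49.3%.

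**Step 4: the pooled reading.** If stratified means one test summed over strata, the statistic is (Σ(b − c))² / Σ(b + c). Strata (6, 1) and (3, 2) give (5 + 1)² / 12 = 3.0. The unstratified table (9, 3) gives (9 − 3)² / 12 = 3.0. Pooling changes nothing.

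**Step 5: a direct comparison.** Score each participant's change in faller status as −1, 0 or +1 and compare two strata of 10 by an exact permutation test. It rejects in about 1–2% of trials when the strata share a true effect of 20% to 50% stopping, and in about 34% when 50% stop in one stratum and 5% in the other (5% starting in both). Fisher's exact test of stopped versus started rejects in only about 2.7% of trials in that second setting, because it looks only at the direction of change among those who changed.

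**The case against.** Four points can be made for the plan.

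- *Chance splits may be rare here.* For 40% to stop falling, at least 40% (8 of 20) must have fallen at baseline, and protocol 10.4 expects few fallers. This stands. A reader might infer that the stratified tests will often produce a false subgroup finding. With the exact test, the documents do not support that for a low-faller sample.
- *No misreading is written down.* A reader might also infer that the plan commits to comparing stratum p-values, or to declaring the fall reduction explained by progression or confined to those who kept exercising. Neither document says so, and no decision rule is given. This stands too, but the absence of a rule leaves the stated question without a method that answers it. Under the pooled reading the split percentages do not apply, yet that reading neither adjusts nor tests influence.
- *A stratum result holds the factor fixed by restriction.* Asking whether falls also dropped among those who stopped exercising is a legitimate descriptive question. This stands, and it is a reason to keep stratum-specific estimates. It does not supply a comparison or an adjusted overall estimate.
- *The analysis is secondary.* Aim #1 is primary, and neither it nor the main Aim #2 test is affected. The planned randomised trial is not said to depend on these strata. This limits the importance of the point, but the remedy is only a change of wording.

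**Conclusion.** The concern holds in a limited form. The stated purpose is to examine influence on the fall result, and neither reading of the stratified McNemar test can do that.

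How misleading the output would be depends on rates the documents do not give. With a large fall reduction (40% to 50% stopping, strata of 10, exact test), identical strata split across the .05 line in about 22% to 40% of trials. At 20% stopping or lower the figure is 1% or less, rising to 15.4% at 20% stopping if the uncorrected chi-square version is used. In the low-faller setting the likelier error is to read two non-significant strata as showing that the factor explains the result, or that it has no influence. Neither conclusion would follow.

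This should be corrected in the SAP, but it does not threaten the primary aim.

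**What to change.** In section 10.3.6 of both documents, replace the stratified McNemar tests with a direct comparison between strata:

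- Compare each participant's change in number of falls between strata by an exact permutation test.
- Report the between-stratum difference with a 95% CI. Report the stratum-specific changes with CIs and without within-stratum p-values.
- Label the analysis exploratory, and call progression and continued exercise possible modifiers, not confounders.
- State that influence is judged only on the between-stratum comparison, and that a non-significant result is not evidence of no influence.

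Fisher's exact test on stopped versus started should not be used as a substitute, for the reason in step 5.

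The cost is SAP and protocol wording; no new data are needed. The price is imprecision. The 34% power for 50% versus 5% stopping was worked out on faller status; the documents give no distribution of fall counts from which to work it out for the number of falls. The confidence interval, not the p-value, should carry the message.
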